STATISTICAL ANALYSIS PLAN

Study Protocol Number: E7080-J081-116/KEYNOTE 524

Study Protocol Title: An Open-Label Phase 1b Trial of Lenvatinib Plus Pembrolizumab in Subjects with Hepatocellular Carcinoma

Date: 22 Oct 2019

Version: Final Version 2.0

Summary of Changes

Revisions to Version 2.0

Date: 22 Oct 2019

Changes	Rationale	Affected Sections
Stated the outline of analysis plan and populations to submit an sNDA/sBLA for accelerated approval (AA) to support the new use of lenvatinib in combination with pembrolizumab for the first-line (1L) treatment of patients with advanced unresectable hepatocellular carcinoma (HCC) not amenable to locoregional treatment.	Updated to clarify the plan for the 1L HCC subjects to support AA applications based on communications with the U.S. Food and Drug Administration (FDA) toward the Type B meeting that was scheduled on 10 Oct 2019.	
 • Section 3 • Section 5 • Section 5.2.1 • Section 5.4 • Section 5.6
Removed the separate description for primary and secondary endpoints and its analyses by DLT part and Expansion part.	Updated to provide analysis results for primary/secondary endpoints using data from the 1L HCC subjects of this study (regardless of DLT/Expansion part), to support AA applications.	
 • Section 5.1.1 • Section 5.1.2 • Section 5.4.1
Added the presentation of unconfirmed response, and the summary for depth of tumor shrinkage in target lesions.	Updated to clarify the analyses for AA applications.	
 • Section 5.4.1
Specified the cutoff date of 31 Oct 2019 for this primary analysis.	Updated to clarify for AA applications.	
 • Section 3 • Section 5 • Section 5.4.1
Specified the sensitivity analyses based on different populations and the supplementary analysis based on different derivation rule for efficacy endpoints.	Added to support AA applications.	
 • Section 3 • Section 5 • Section 5.2.1 • Section 5.4.4 • Section 8.2
Added concordance analysis between independent imaging review and investigator.	Added to support AA applications.	
 • Section 5.4.5
Removed the summary of number of cycles, dose intensity, relative dose intensity, and dose interruption of pembrolizumab.	Updated to align with other pembrolizumab studies.	
 • Section 5.6.1
Added the summary for clinically significant TEAEs (CSAE) for lenvatinib, and TEAEs of special interest (AEOSI) for pembrolizumab.	Added to support AA applications.	
 • Section 5.6.3
Defined serious adverse events that develop from 31 days up to 120 days after the subject's last dose of study drug as treatment-emergent SAEs.	Updated to be consistent with protocol amendment 05.	
 • Section 8.3
Minor editorial changes	To correct errors or clarify text	
 • Throughout

2 LIST OF ABBREVIATIONS AND DEFINITIONS OF TERMS

Abbreviation	Term
AA	accelerated approval
ADA	anti-drug antibody
AE	adverse event
AEOSI	adverse events of special interest
AFP	alpha-fetoprotein
ATC	anatomical therapeutic chemical
BCLC	Barcelona Clinic Liver Cancer
BOR	best overall response
BW	body weight
CI	confidence interval
CR	complete response
CRF	case report form
CSAE	clinically significant adverse event
CSR	clinical study report
CTCAE	common toxicity criteria for adverse events
DCR	disease control rate
DOR	duration of response
DLT	dose-limiting toxicity
ECG	electrocardiogram
ECOG	Eastern Cooperative Oncology Group
FDA	Food and Drug Administration
HBcAb	hepatitis B core antibody
HBsAb	hepatitis B surface antibody
HBsAg	hepatitis B surface antigen
HBV	hepatitis B virus
HCC	hepatocellular carcinoma
HCV	hepatitis C virus
HRQoL	Health Related Quality of Life
IIR	independent imaging review
IV	intravenous
LLT	lower level term
LVEF	left ventricular ejection fraction
MedDRA	Medical Dictionary for Regulatory Activities

Abbreviation	Term
mRECIST	modified RECIST
NE	not evaluable
NYHA	New York Heart Association
ORR	objective response rate
OS	overall survival
PD	pharmacodynamics
PD	progressive disease
PD-L1	PD-1 ligand 1
PFS	progression free survival
PK	pharmacokinetics
PR	partial response
PS	performance status
PT	preferred term
Q3W	every 3 weeks
QD	once daily
QOD	every other day
QT	QT interval
QTc	QT interval corrected for heart rate
RECIST	response evaluation criteria in solid tumor
SAP	statistical analysis plan
SAE	serious adverse event
SD	stable disease
SI	système international
sBLA	supplemental Biologics License Application
sNDA	supplemental New Drug Application
SOC	system organ class
TEAE	treatment-emergent adverse event
TEMAV	treatment-emergent markedly abnormal laboratory value
TLG	tables, listings, and graphs
TNM	tumor-node-metastasis
TTP	time to progression
TTR	time to response
WHO DD	World Health Organization drug dictionary

3 INTRODUCTION

Eisai Protocol E7080-J081-116/KEYNOTE 524 (Study 116/KN524) is a multicenter, open-label Phase 1b study of lenvatinib (E7080) plus pembrolizumab in subjects with advanced/unresectable hepatocellular carcinoma (HCC). As discussed with the U.S. Food and Drug Administration (FDA) toward the Type B meeting (that was scheduled on 10 Oct 2019), Eisai and Merck is planning to submit an sNDA/sBLA for accelerated approval (AA) to support the new use of lenvatinib in combination with pembrolizumab for the first-line (1L) treatment of patients with advanced unresectable hepatocellular carcinoma not amenable to locoregional treatment. Based on communications with the FDA, statistical analyses tables, listings, and graphs (TLGs) will be produced with the data up to the cutoff date of 31 Oct 2019. For the 1L HCC subjects, the first 80 subjects will be used for the primary efficacy evaluation and all 100 subjects will be included in an efficacy sensitivity analysis as well as the safety assessment. A primary Clinical Study Report (CSR) will be prepared for these 1L HCC subjects to support the AA application. The CSR will also include all HCC subjects enrolled into Study 116, including the additional 4 subjects with prior anticancer medication as per the protocol.

The purpose of this statistical analysis plan (SAP) is to describe the procedures and the statistical methods that will be used to analyze and report results for Study 116/KN524 except for pharmacokinetic, pharmacodynamics, pharmacogenomics, biomarker and Health Related Quality of Life (HRQoL) analysis that will be performed separately from the primary CSR. This SAP is based on the clinical study protocol amendment 05 (dated 17 Jan 2019).

3.1 Study Objectives

3.1.1 Primary Objective

- To evaluate the tolerability and safety for combination of lenvatinib plus pembrolizumab in subjects with hepatocellular carcinoma (HCC).
- (Expansion part) To evaluate objective response rate (ORR) and duration of response (DOR) by modified Response Evaluation Criteria In Solid Tumors for HCC (mRECIST) and RECIST 1.1 based on independent imaging review (IIR)

3.1.2 Secondary Objectives

- (DLT evaluation Part) To evaluate ORR and DOR by mRECIST (based on investigator review and IIR), and by RECIST1.1 based on IIR
- (Expansion Part) To evaluate ORR and DOR by mRECIST based on investigator review
- To evaluate the following efficacy endpoints by mRECIST (based on investigator review and IIR) and RECIST1.1 (based on IIR):
 - Progression-free survival (PFS)
 - Time to Progression (TTP)

- Time to Response (TTR)
- Overall survival (OS)
- To assess the pharmacokinetic (PK) profile of lenvatinib and pembrolizumab
- To detect anti-drug antibodies for pembrolizumab (ADA)

3.1.3 Exploratory Objective

- To evaluate the following efficacy endpoints by mRECIST (based on investigator review and IIR) and RECIST1.1 (based on IIR):
 - Disease control rate (DCR)
 - Clinical benefit rate (CBR)
- To evaluate the impact of treatment on Health Related Quality of Life (HRQoL) for subjects treated using the European Organisation for Research and Treatment of Cancer (EORTC) QLQ-C30, HCC-specific EORTC QLQ-HCC18 questionnaire and European Quality of Life questionnaire.
For the subjects in Expansion part added as of the protocol Amendment 03, HRQoL will be evaluated using the EORTC QLQ-C30 and the HCC specific supplement QLQ-HCC18. HRQoL will also be evaluated using the generic EuroQol five dimension five level (EQ-5D-5L) questionnaire.
- To investigate the relationship between candidate biomarkers and anti-tumor activity of lenvatinib in combination with pembrolizumab:
 - To explore blood and tumor markers (such as PD-L1 expression levels, cytokine and angiogenic factor profiling), and immune cell profiling and evaluate their relationship with clinical outcomes including anti-tumor activity of lenvatinib in combination with pembrolizumab

3.2 Overall Study Design and Plan

This is an open-label Phase 1b study. This study will evaluate the tolerability and safety of lenvatinib in combination with pembrolizumab in subjects with HCC.

This study will begin with lenvatinib 12 mg (body weight [BW] ≥ 60 kg) or 8 mg (BW < 60 kg) /day orally and pembrolizumab 200 mg (every 3 weeks [Q3W], intravenous [IV]) in subjects with HCC. Tolerability of this dose level will be evaluated by dose limiting toxicities (DLTs) during the first cycle (21-day treatment cycle).

In this dose level, 3 subjects will be enrolled first. If 0 or 1 of 3 subjects in a given dose level cohort experiences a DLT, then 3 more subjects will be enrolled into that dose level. If 0 or 1 of 6 subjects in a given dose level cohort experiences a DLT, the dose level will be considered tolerable. Additional 4 subjects can be enrolled without DLT evaluation if further

safety information is considered necessary based on the discussions between the sponsor and investigators.

Enrollment will be interrupted if 2 or more DLTs are observed in this dose level, and after sponsor and investigators' review, enrollment may continue for up to 6 subjects based on the nature and severity of the DLTs. Once 6 subjects are enrolled, after sponsor and investigators' review regarding the nature and severity of the DLTs, an additional 4 subjects (10 subjects in total for DLT evaluation) will be enrolled, and that dose level will be considered to be tolerable if DLT is observed in 3 or less of the 10 subjects in total. An independent medical advisor as third party may be consulted for the review as needed.

In this dose level, at least 3 subjects treated with lenvatinib 12 mg once daily (QD) and pembrolizumab 200 mg Q3W IV (BW \geq 60 kg) need to be included in the 6 subjects for DLT evaluation. (In case of the 10 subjects for DLT evaluation, at least 5 subjects (BW \geq 60 kg) treated with lenvatinib 12 mg QD and pembrolizumab 200 mg Q3W IV need to be included.)

Cohort of reduction to lower dose level (lenvatinib) or study discontinuation will be considered, if this dose level (12 mg [BW \geq 60 kg] or 8 mg [BW <60 kg] lenvatinib plus 200 mg pembrolizumab) is not tolerable, upon discussions between the sponsor and investigators, and the protocol will be amended as necessary. An independent medical advisor as third party may be consulted for the consideration as needed.

If there is a potential subject who is not evaluable for DLT (eg, subject who fails to administer \geq 75% of the planned dosage of lenvatinib due to a reason other than treatment related toxicity during Cycle 1), the investigator and sponsor will discuss whether or not to include the subject in the DLT Analysis Set. If subject is not evaluable for DLT, then the subject will be replaced.

For determination of the recommended phase 2 dose, all episodes of Grade 3 or 4 thrombocytopenia and neutropenia beyond Cycle 1 will be taken into consideration.

If the dose level is confirmed to be tolerable, an additional (approximately) 20 subjects will be enrolled for consolidation of PK data and safety and efficacy as the **Expansion part**. As of Amendment 03, the Expansion part may be further expanded up to approximately 94 subjects. The decision to expand enrollment will be based on the results of 2 interim analyses that will take place when 20 (6 subjects for DLT evaluation part plus 14 subjects for Expansion part) and 56 subjects (6 subjects for DLT evaluation part plus 50 subjects for Expansion part) have sufficient follow-up to be evaluated for response. The decision to expand enrollment will be assessed by mRECIST based on investigator review. At least 5 subjects (BW \geq 60 kg) treated with lenvatinib 12 mg QD and at least 5 subjects (BW<60 kg) treated with lenvatinib 8 mg QD will be included in Expansion part.

The study will be conducted in 3 phases: a Pretreatment Phase, a Treatment Phase, and an Extension Phase.

- The **Pretreatment Phase** will last no longer than 28 days and will include a Screening Period and a Baseline Period.
- The **Treatment Phase** consists of the first cycle (21 days) for each subject. The Treatment Phase for each subject ends after completing Cycle 1 of treatment or if they discontinue early. Those subjects who discontinue study treatment in Cycle 1 transition to the Off Treatment (Off-Tx) Visit of the Follow-up Period of the Extension Phase. Those who complete Cycle 1 transition to the Treatment Period of the Extension Phase.
- The **Extension Phase** consists of 2 periods, the Treatment Period and the Follow-up Period. Subjects still receiving study treatment at the end of the Treatment Phase will continue to receive the same study treatment in the Treatment Period of the Extension Phase. Subjects will continue to receive study treatment until disease progression, development of unacceptable toxicity, withdrawal of consent, or sponsor termination of the study. Those subjects who discontinue study treatment transition to the Off-Tx Visit of the Follow-up Period of the Extension Phase.

[figure not shown]

Figure 1 Study Design

4 DETERMINATION OF SAMPLE SIZE

The original sample size in this study was approximately 30 subjects (N=6 to 10 for DLT evaluation part and N=20 for Expansion part). This was not based on statistical power considerations.

The sample size in the Expansion part was 20 evaluable subjects. The associated 2-sided 95% CIs for the ORR of 10% to 90% for 20 subjects are provided in Table 1.

Table 1 2-sided 95% Confidence Interval for the ORR of 10% to 90% (20 subjects)

ORR (N=20)	95% CI
10%	(0.012, 0.317)
20%	(0.057, 0.437)
30%	(0.119, 0.543)
40%	(0.191, 0.639)
50%	(0.272, 0.728)
60%	(0.361, 0.809)
70%	(0.457, 0.881)
80%	(0.563, 0.943)
90%	(0.683, 0.988)

CI = confidence interval, ORR = objective response rate.
95% CI is estimated using Clopper-Pearson method.

As of Amendment 03, the Expansion part may be further expanded up to approximately 94 evaluable subjects. For this expansion decision, 2 interim analyses will take place when 20 (6 subjects for DLT evaluation part plus 14 subjects for Expansion part) and 56 subjects (6 subjects for DLT evaluation part plus 50 subjects for Expansion part) have sufficient follow-up to be evaluated for response. The decision to expand enrollment will be based on the results of 2 interim analyses, which will spend $\beta=0.012$ and $\beta=0.024$ at the first and second interim analyses, respectively. The decision to expand enrollment will be assessed by mRECIST based on investigator review.

Based on an assumption of H0: 25% ORR and H1: 45% ORR, the 100-subject design with two futility analyses has approximately 96% statistical power at 2-sided $\alpha = 0.02$ (that corresponds to 1-sided $\alpha=0.01$). At the first interim analysis (N=20), if there are more than 5 responses, then approximately 36 additional subjects will be enrolled. At the second interim analysis (N=56), if there are more than 16 responses, approximately 44 additional subjects will be enrolled. If there are 5 or fewer responses at the first interim analysis (N=20) or 16 or fewer responses at the second interim analysis (N=56), the sponsor may decide whether to expand enrollment based on clinical outcome (eg, DOR).

The boundaries for the decision to expand enrollment in Expansion part are presented in Table 2.

Table 2 Boundaries for the Decision to Expand Enrollment in the Expansion Part

Analysis Number	Cumulative β Spent	Objective Response Rate	P-value
Interim Analysis 1 (N=20)	0.012	0.258	0.933
Interim Analysis 2 (N=56)	0.024	0.301	0.376
Final Analysis (N=100)	0.041	0.351	0.020

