5 STATISTICAL METHODS

Based on communications with the FDA toward the Type B meeting (that was scheduled on 10 Oct 2019), efficacy data up to the cutoff date of 31 Oct 2019 from the first 80 1L HCC subjects (with projected median study follow-up of approximately 12 months, based on 30 Jun 2019 data cutoff) will be the primary data set supporting the AA applications of the combination of lenvatinib plus pembrolizumab for the 1L treatment of patients with advanced unresectable HCC not amenable to locoregional treatment. The data from all 100 1L HCC subjects (with projected median study follow-up of approximately 10.5 months, based on 30 Jun 2019 data cutoff) will be analyzed as a sensitivity analysis for key efficacy endpoints as well as for the overall safety assessment. In addition, the data from the first 60 1L HCC subjects (with projected median study follow-up of approximately 15.5 months, based on 30 Jun 2019 data cutoff) will also be presented for key efficacy endpoints as an efficacy sensitivity analysis to assess the outcome in the subjects with longer duration of follow-up.

Therefore, statistical analyses for the CSR described hereafter will be performed on the 1L HCC subjects to support AA applications, as well as on all HCC subjects including the four subjects with prior anticancer medication as per the protocol, unless otherwise specified. Data from 1L HCC subjects will be presented in a column labeled as “HCC-1L”, and data from all HCC subjects (including subjects with prior anticancer medication) will be presented in a column labeled as “All HCC”. The analysis tables will minimally have the following headers.

Study subjects (eg, subject disposition, baseline characteristics, etc.) tables

HCC-1L		All HCC		
First 80 (N=80)	All (N=100)	DLT Part (N=6)	Expansion Part (N=98)	Overall (N=104)

Efficacy/Safety tables for the 1L HCC subjects to support AA applications

First 80 HCC-1L (N=80)	All HCC-1L (N=100)	First 60 HCC-1L (N=60)
---------------------------	-----------------------	---------------------------

Efficacy/Safety tables for all HCC subjects (including subjects with prior anticancer medication) as per the protocol

DLT Part (N=6)	Expansion Part (N=98)	Overall (N=104)
-------------------	--------------------------	--------------------

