5.2.1 Definitions of Analysis Sets

DLT Analysis Set will include all subjects (except for the Expansion part) who have completed Cycle 1 without major protocol deviation with at least 75% of study drug compliance and are assessed for DLT, and subjects who have experienced DLT during Cycle 1. This will be the analysis set to determine tolerability.

Safety Analysis Set and **Efficacy Analysis Set** will include all subjects who received at least 1 dose of study drug. Safety Analysis Set will be used for safety evaluations. Efficacy Analysis Set will be used for efficacy evaluations, as well as for demographic and baseline characteristics, etc.

These analysis sets will be applied to the following populations depending on the purpose, as explained above in the beginning of [Section 5](#).

FOR THE 1L HCC SUBJECTS TO SUPPORT AA APPLICATIONS

Efficacy Analysis Set in:

- First 80 HCC-1L subjects (N=80; for primary analysis)
- All HCC-1L subjects (N=100; for sensitivity analysis)

- First 60 HCC-1L subjects (N=60; for sensitivity analysis)

Safety Analysis Set in:

- First 80 HCC-1L subjects (N=80; for summary of extent of exposure only)
- All HCC-1L subjects (N=100; for all safety analyses)

**FOR ALL HCC SUBJECTS (INCLUDING 4 SUBJECTS WITH PRIOR ANTICANCER MEDICATION)
AS PER THE PROTOCOL**

Efficacy Analysis Set/Safety Analysis Set in:

- Subjects from DLT part (N=6)
- Subjects from Expansion part (N=98)
- Overall (N=104)

PK Analysis Set includes all subjects who have received at least 1 dose of lenvatinib and pembrolizumab, and have evaluable concentration data.

The number (percentage) of subjects included in each analysis set will be presented. Subject data listings will be provided.

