5.3.3 Multiple Comparisons/Multiplicity

No statistical comparison is planned in this study.

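### Do the 96% power and the 0.351 final boundary of the 100-subject design have to be detached from the primary ORR analysis in the first 80 first-line subjects?

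*SAP*

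**What the plan says.** Section 4 (Determination of Sample Size), largely repeated in Section 6 (Interim Analyses), describes a one-sample design dated to Amendment 03. Under it "the Expansion part may be further expanded up to approximately 94 evaluable subjects", which with the 6 subjects of the DLT part makes 100. The design statement reads: "Based on an assumption of H0: 25% ORR and H1: 45% ORR, the 100-subject design with two futility analyses has approximately 96% statistical power". The alpha attached to it is 0.02, 2-sided. Two futility looks, at 20 and 56 subjects, steer the decision to expand enrolment, using mRECIST by investigator review. If a count falls short, the sponsor may still decide to expand. Table 2, titled for the expansion decision, has a last row for N=100 with cumulative beta 0.041, ORR 0.351 and p-value 0.020.

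Version 2.0 then defines the analysis for the accelerated-approval application. Section 3 says that "the first 80 subjects will be used for the primary efficacy evaluation". Section 5 says that efficacy data from those 80 first-line subjects "will be the primary data set supporting the AA applications of the combination of lenvatinib plus pembrolizumab". Section 5.4.1 analyses ORR by mRECIST and RECIST 1.1 under independent review and reports it with an exact 2-sided 95% CI. Section 5.2.1 gives all 100 first-line subjects the role of a sensitivity set. Section 5.3.3 adds: "No statistical comparison is planned in this study".

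**The concern.** The plan contains one set of hypotheses, one alpha, one power figure and one final threshold. All of them belong to an analysis that is no longer primary. The primary number is now 80, the population is restricted to first-line subjects, and the reader is independent review rather than the investigator. No sentence separates the two.

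Three features add to the unease:

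- Two different groups carry the number 100. The design's 100 is 6 DLT plus about 94 Expansion subjects with no stated first-line restriction; the All HCC-1L set is also 100.
- At N=100 there is no further enrolment to decide, so the last row of a table about expansion looks like an end-of-study criterion.
- A final p-value boundary sits awkwardly beside Section 5.3.3.

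If the doubt were real, someone could later quote 96% power or a 35.1% threshold as a prespecified standard for the ORR submitted for accelerated approval, although neither was calculated for it.

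**Working it through.** **1. Do the printed figures hold for the design they describe?**

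Inputs from Section 4 and Table 2: p0 = 0.25, p1 = 0.45, 1-sided alpha 0.01, looks at n = 20, 56 and 100, boundaries 0.258, 0.301 and 0.351.

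Final boundary, normal approximation with null variance: 0.25 + 2.326 × √(0.25 × 0.75 / 100) = 0.25 + 2.326 × 0.0433 = 0.3507. Table 2 prints 0.351.

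Two-sided p-values at the boundaries, from z = (boundary − 0.25) / √(0.1875 / n):

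| n | z | p | printed |
|---|---|---|---|
| 20 | 0.008 / 0.0968 = 0.083 | 0.934 | 0.933 |
| 56 | 0.051 / 0.0579 = 0.881 | 0.378 | 0.376 |
| 100 | 0.101 / 0.0433 = 2.33 | 0.0197 | 0.020 |

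Power: the stated cumulative beta gives 1 − 0.041 = 0.959, the plan's approximate 96%. Recomputed:

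- Three-look normal model, null variance, Table 2 boundaries: cumulative beta 0.0346, power 96.5%.
- Exact binomial, futility ignored because it is not binding: 0.351 means at least 36 of 100; P(X ≥ 36 | 0.25) = 0.0094 and P(X ≥ 36 | 0.45) = 97.3%.
- Exact binomial with the futility counts (more than 5 of 20, more than 16 of 56) treated as binding: 92.3%. Section 4 does not make them binding.

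So the 96% is a fair description of the 100-subject design as written.

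**2. Does the SAP attach these figures to the first-80 analysis?**

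| Item | Sections 4 and 6, Table 2 | Sections 5, 5.2.1, 5.4.1 |
|---|---|---|
| Purpose | decision to expand enrolment, Amendment 03 | primary efficacy data for accelerated approval |
| Subjects | 6 + about 94 = 100, no first-line restriction stated | first 80 first-line |
| Reader | investigator mRECIST for the expansion decision; not stated for the final row | independent review, mRECIST and RECIST 1.1 |
| Output | boundary and p-value | estimate and exact 95% CI |
| Null rate, alpha, threshold | 25%, 2-sided 0.02, 0.351 | none |

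Nothing in the right-hand column refers to the left. The two groups of 100 can be told apart from Section 5: All HCC has 6 DLT + 98 Expansion = 104 subjects, and 104 − 4 with prior anticancer medication = 100 first-line subjects. The design's 100 corresponds to the 104, not to the 100 first-line subjects.

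**3. What would change if the plan carried a disclaimer?**

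The planned output is a Clopper-Pearson interval, which depends only on the responder count and N. At an observed 45% it is 33.8% to 56.5% for 36/80 (width 22.7 points) and 35.0% to 55.3% for 45/100 (width 20.2 points). Both are the same with or without the sentence.

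**4. What if a reader wrongly carried 0.351 over to 80 subjects?**

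0.351 × 80 = 28.08, so at least 29 of 80. The exact 95% CI is 24.7% to 46.5% for 28/80 and 25.8% to 47.8% for 29/80. The misapplied threshold and the planned interval therefore part from 25% at the same count. The 1-sided error at 29/80 is 0.0166, above the design's 0.01, so 0.351 does not keep its alpha at N=80. That matters only if the plan tested with it, and it does not.

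**The case for a change.** The best case for a change is that the Table 2 title explains the two interim rows but not the last one. The 96% power depends on that last row being a test. A section on sample size that gives neither power nor precision for the primary 80 leaves the status of 0.351 to inference. Section 7 reports the added accelerated-approval plan without mentioning the sample-size basis. One sentence would be cheap and would prevent a convenient reading after the results are known.

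Part of this stands. The final row is unexplained, its reader is not named, and no sentence states its status. The rest does not carry the point. A sample-size section properly records the design under which subjects were enrolled, and an estimate in a later-defined subset does not need its own power. Section 5.3.3 may mean only that no groups are compared; read literally, it too points away from any test against 25%. Section 7 places the accelerated-approval analyses alongside the protocol's, not in their place.

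Power figures for 80 subjects can be produced, for example 92.9% for at least 30/80 at 2-sided 0.02, but they describe a test that the plan does not contain. A drafted statement that 0.351 is not a success criterion would also decide something for the sponsor that this document alone cannot establish.

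**Conclusion.** No change to the plan follows. No stated figure is shown to be wrong for the design it is attributed to. The SAP never claims 96% power, or a 35.1% threshold, for the ORR in the first 80 first-line subjects. Analysts following Section 5.4.1 would produce the same estimate, the same exact 95% CI and the same data set with or without a disclaimer, so the effect on the results is zero.

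What remains is a labelling gap. The sponsor could, if it wished, footnote Table 2 to say whether the N=100 row is only a record of the enrolment design, and that its 100 is not the All HCC-1L set.

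The conclusion rests on two assumptions: that futility is non-binding, as Section 4 says, and that the protocol, which was not available for this check, does not make the N=100 row a success criterion for the first-80 analysis.

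### The stated beta (0.012/0.024/0.041) and 96% power do not belong to the written count rules: exact beta is 0.055/0.060/0.077, and power is 92.3% if the rules are followed or 97.3% if they are overridden

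*SAP*

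**What the plan says.** SAP Section 4 sets out the design: "Based on an assumption of H0: 25% ORR and H1: 45% ORR", two interim looks at 20 and 56 subjects, a total of 100, and a one-sided alpha of 0.01. It states that "the 100-subject design with two futility analyses has approximately 96% statistical power". Section 6 repeats the statement.

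Enrolment goes on if responses exceed 5 of 20, and then 16 of 56. The other branch opens with this condition: "If there are 5 or fewer responses at the first interim analysis (N=20) or 16 or fewer responses at the second interim analysis (N=56"). It does not close enrolment automatically. What follows instead is that "the sponsor may decide whether to expand enrollment based on clinical outcome (eg, DOR"). So these are one-sided counts, and they are non-binding.

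On error spending, the prose refers to the two looks "which will spend $\beta=0.012$ and $\beta=0.024$ at the first and second interim analyses, respectively". Table 2 gives the same values, plus 0.041 at the final analysis, in a column headed "Cumulative β Spent". Its ORR boundaries are 0.258, 0.301 and 0.351, and its p-values are 0.933, 0.376 and 0.020.

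Elsewhere, Section 5.2.1 names the primary efficacy population as "First 80 HCC-1L subjects (N=80; for primary analysis"), and Section 5.3.3 says: "No statistical comparison is planned in this study".

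**The concern.** The beta tabled at a futility boundary is normally read as the probability that a drug with the target ORR falls on the wrong side of it. At the first look this is a single binomial tail, P(X ≤ 5) with n = 20 and p = 0.45. It is plainly larger than 0.012, because the term for exactly 5 responses is already 0.036. If the interim betas do not fit the count rules, the total beta and the power derived from it are in doubt too.

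At stake is whether Sections 4 and 6 describe the design correctly in a SAP written to support an accelerated approval application. A reader would conclude that the first look carried about a 1% risk of wrongly falling below the expansion line when, for the rule as written, the risk was above 5%.

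**Working it through.** **Inputs (SAP Section 4 and Table 2).** ORR of 0.25 under H0 and 0.45 under H1; looks at n = 20, 56 and 100; futility at X20 ≤ 5 or X56 ≤ 16; final ORR boundary 0.351. The SAP gives no final count. Since 0.351 × 100 = 35.1, success is taken as X100 ≥ 36. The interim counts agree with the tabled ORRs (0.258 × 20 = 5.16; 0.301 × 56 = 16.86), so it is the beta column that does not fit.

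**1. Reproducing the plan's figures**

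*P-values.* z = (boundary − 0.25)/√(0.25 × 0.75/n) gives 0.083, 0.881 and 2.332. The two-sided p-values are 0.934, 0.378 and 0.0197, against the tabled 0.933, 0.376 and 0.020. Table 2 therefore uses two-sided p-values with the null variance.

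*Beta and power.* The stated power agrees with the table: 1 − 0.041 = 95.9%. The SAP names no method, so several normal approximations were tried at the tabled ORR boundaries with a true ORR of 45%. The two-sided versions were simulated with 4 million runs.

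| Version | Cumulative beta | Power |
|---|---|---|
| SAP Table 2 | 0.012 / 0.024 / 0.041 | about 96% |
| One-sided, H0 variance | 0.024 / 0.027 / 0.035 | 96.5% |
| One-sided, H1 variance | 0.042 / 0.050 / 0.064 | 93.6% |
| Two-sided inner wedge, H0 variance | 0.008 / 0.012 / 0.021 | 97.9% |
| Two-sided inner wedge, H1 variance | 0.011 / 0.023 / 0.040 | 96.0% |

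In an inner wedge, futility means that the observed ORR lies close to 25% on either side. Only this form, with the H1 variance, comes near all three stated betas. No one-sided version gives 0.012 at n = 20. That the figures came from such a design is an inference.

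A wedge is not the written rule. At the first look it covers only ORRs within 0.008 of 0.25, that is 0.242 to 0.258, or exactly 5 of 20 (probability 0.0365 at 45% ORR). It leaves out 0 to 4 of 20 (probability 0.0189), which the text counts as futility. Together these make 0.0365 + 0.0189 ≈ 0.055.

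**2. Exact calculation for the written rules at 45% ORR**

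- First look: P(X20 ≤ 5) = 0.0553.
- Second look: P(X20 > 5 and X56 ≤ 16) = 0.0042; cumulative 0.0596.
- Final: P(both looks passed and X100 ≤ 35) = 0.0178; cumulative 0.0773.
- Power with both rules followed: 1 − 0.0773 = 0.9227.

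| Cumulative beta | SAP | Exact |
|---|---|---|
| First look (n = 20) | 0.012 | 0.055 |
| Second look (n = 56) | 0.024 | 0.060 |
| Final (n = 100) | 0.041 | 0.077 |

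The first-look ratio is 0.0553/0.012 ≈ 4.6.

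**3. Allowing for the non-binding rules (exact, 45% ORR)**

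| Rules followed | Power | Loss |
|---|---|---|
| Neither: P(X100 ≥ 36) | 97.3% | – |
| Second look only | 96.9% | 0.4 points |
| First look only | 92.5% | 4.8 points |
| Both | 92.3% | 5.0 points |

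**4. Type I error at 25% ORR.** P(X100 ≥ 36) = 0.0094, or 0.0077 with both futility rules followed. Both are below 0.01.

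**5. Sensitivity to the final count.** If 35 of 100 counted as success, power with both rules followed would be 93.0%, still short of 96%, and the one-sided alpha without futility stopping would rise to 0.0164. The betas at the two interim looks do not depend on the final count.

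**6. Wording.** Read as increments, the prose gives 0.012 + 0.024 = 0.036 by the second look; read as cumulative, as in Table 2, it gives 0.024. Neither matches 0.060.

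**The case against.** The best defence is that 96% is not a slip. A normal-approximation design at Table 2's boundaries returns 96.0%, the SAP says approximately, and the figure lies between 92.3% and 97.3%. Because the sponsor may expand enrolment below either line, type II error arises only if enrolment really stops. If only the second rule were followed, power would be 96.9%. It can also be said that the inner wedge is conjecture, that the count of 36 is not in the SAP, that the column heading in Table 2 already settles the cumulative reading, and that nothing still to be done depends on any of this.

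Much of this stands. The wedge is an inference and the finding does not need it. The count of 36 is derived. The wording point is editorial. The practical consequence is small.

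The defence does not rescue the beta column. Spending beta at a look supposes that the rule is followed, and 0.012 is tabled against a boundary whose exact probability under the written rule is 0.055. Non-binding status turns power into a range but leaves that probability unchanged. A power of 96% that follows from the stated betas describes neither following both rules nor overriding both.

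**Conclusion.** The point holds. For the count rules as written, exact cumulative beta at 45% ORR is 0.055/0.060/0.077, against the stated 0.012/0.024/0.041. Power is 92.3% if both rules are followed, 3.7 points below the stated 96%, and 97.3% if both are always overridden. Almost all of the loss comes from the first look.

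The first-look figure rests only on the written count and the stated 45%. Total beta and power also rest on reading the 0.351 boundary as 36 or more of 100, and the beta values suppose that the futility rules are followed. The type I error claim is sound.

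The effect is confined to the design record. The SAP already tabulates 104 subjects, so both looks are past; no statistical comparison is planned; and the primary efficacy analysis is ORR with an exact confidence interval, and DOR, in the first 80 first-line subjects. No estimate, interval or remaining enrolment decision changes. The figures should still be corrected, because anyone can disprove 0.012 with one binomial calculation and the correction costs almost nothing.

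**What to change.** Add to Sections 4 and 6, and as a footnote to Table 2, text such as:

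> Calculated retrospectively for the count rules (5 or fewer of 20; 16 or fewer of 56; success at 36 or more of 100, derived from the 0.351 boundary), exact binomial cumulative beta at 45% ORR is 0.055, 0.060 and 0.077 if the futility rules are followed. Power is about 92% if both rules are followed and about 97% if they are always overridden.

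If 0.012/0.024/0.041 and 96% are kept for the record, state the method and convention that produced them. Reword the prose in both sections to say that cumulative beta is 0.024 by the second interim analysis, in line with Table 2.

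The cost is a few sentences and one footnote. The stated power becomes a range. No patients, analyses or enrolment rules change.
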